### **2.3.2 Baseline, Changes from Baseline and Direction of Differences**

The latest measurement taken on or before day 1 prior to the first injection will be the baseline measurement. In addition, within each treatment cycle, “cycle baseline” is defined as the most recent evaluation prior to the current cycle’s treatment. Changes from baseline will be based on the day 1 baseline (rather than cycle baseline) unless otherwise stated.

Change from baseline will be calculated as followup minus baseline. The interpretation of a positive or negative change from baseline is specific to the outcome measure and will be discussed as needed. Treatment differences will be reported as BOTOX minus placebo and as BOTOX (higher total dose) minus BOTOX (lower total dose).

### **2.3.3 Time Variables**

Study days will be calculated based on day 1 as follows:

- Study day = visit date minus date of day 1 plus 1.

Treatment cycle days will be calculated as follows:

- Treatment cycle day = visit date minus date of treatment cycle injection plus 1.

In general, there will be no substitution for missing time or date. However, any partial information will be utilized to its full extent wherever sensible. For example, a medication may be classified as a pre-study medication if the partial information of the medication ending date with only month and year permits a determination that the medication ended prior to the injection date of the study medication.

If, for some reason, a partial visit date exists, it will be imputed on a case-by-case basis as necessary.

Partial adverse event onset date will be imputed as follows: 1) if day is missing but month is not, impute the date as the first day of the month; 2) if both day and month are missing, impute the date as 01 Jan; 3) if imputed partial onset date is before the first treatment for adverse event with onset after treatment, impute the date as the first injection date; 4) if imputed partial onset date is before period 2 for adverse event with onset during period 2, impute the date as the day 180 visit date. Imputed partial adverse event onset date will only be used to determine the adverse event onset cycle.

Partial adverse event stop date will be imputed as follows: 1) if day is missing but month is not, impute the date as the last day of the month; 2) if both day and month are missing, impute the date as 31 Dec.

The date of first increase in severity to moderate, if a partial date, will be imputed as follows: 1) if day is missing but month is not, impute the date as the 15th of the month; 2) if both day and month are missing, impute the date as 15 June; 3) if imputed partial date is before the first treatment while the maximum severity during pretreatment period is mild, impute the date as the first injection date; 4) if imputed partial date is during study period 1 (on or after first treatment date but before day 180 visit date) while the maximum severity during study period 1 is mild, impute the date as the day 180 visit date.

The date of first increase in severity to severe, if a partial date, will be imputed as follows: 1) if day is missing but month is not, impute the date as the 15th of the month; 2) if both day and month are missing, impute the date as 15 June; 3) if imputed partial date is before the first treatment while the maximum severity during pretreatment period is mild or moderate, impute the date as the first injection date; 4) if imputed partial date is during study period 1 (on or after first treatment date but before day 180 visit date) while the maximum severity during study period 1 is mild or moderate, impute the date as the day 180 visit date.

Imputed partial adverse event dates will only be used to determine TEAE. All partial dates will be listed “as is” in the data listings.

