### 1.1 Primary Study Objectives and Design

The objectives of this study are to evaluate the safety and efficacy of a range of doses of BOTOX for the treatment of subjects with bilateral masseter muscle hypertrophy (MMH).

This study is a multicenter, randomized, double-blind, placebo-controlled, up to 2-treatment, dose escalation study. BOTOX or placebo will be administered intramuscularly to the bilateral masseter muscles (6 total injections, 3 injections/masseter). The initial BOTOX total dose will be 24 U (12 U/masseter) and the maximum BOTOX total dose will be 96 U (48 U/masseter). Stratification will be by baseline (day 1) Masseter Muscle Prominence Scale (MMPS) grade at baseline (day 1). The planned dose escalation is as follows:

Cohort	Total Dose	Sample Size	Total Subjects/Cohort
1	24 U	N=40	50
	placebo	N=10	
2	48 U	N=40	50
	placebo	N=10	
3	72 U	N=40	50
	placebo	N=10	
4	96 U	N=40	50
	placebo	N=10	

The second treatment is only allowed at the day 180 visit. Subjects will receive the same treatment as they received at the day 1 visit.

Subjects who meet the following retreatment criteria at the day 180 visit will receive a second treatment:

- Allergan written notification allowing retreatment of the current cohort

- subject has marked (grade 4) or very marked (grade 5) bilateral masseter muscle hypertrophy, as assessed by the investigator using the MMPS
- females of childbearing potential must have a negative urine pregnancy test prior to treatment

The primary efficacy variable, change from baseline in lower facial volume ( $\text{cm}^3$ , note that  $1\text{cm}^3=1\text{mL}$ ), is calculated from VECTRA M3 digital photography system 3D image models

[REDACTED]

The primary safety analysis is the calculation of incidence of treatment emergent adverse events (TEAE) for the entire study period, as well as for each treatment cycle.

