## **6.2 Adverse Events**

Adverse events will be coded from the verbatim text into preferred term (PT) and the primary system organ class (SOC) by using the MedDRA dictionary.

Adverse events are collected both for the screening/baseline period pretreatment (which are referred to as pretreatment AE) and for the followup period after treatment is initiated (which are referred to as postbaseline AE).

A treatment emergent adverse event (TEAE) is an adverse event with onset after the initiation of study treatment, or an adverse event with onset prior to study treatment that worsened in severity, or became serious after the initiation of study treatment.

A TEAE for a specific treatment cycle is an adverse event with onset after the initiation of study treatment for the specific cycle, or an adverse event with onset prior to the cycle that worsened in severity during the cycle, or became serious after the initiation of study treatment for the specific cycle.

In each of the analysis periods (entire study or by treatment cycle), a specific TEAE will only count once per subject, associated with its worst severity during the time period of interest. Unless stated otherwise, the methods of analyses described in this section will be applied to each of the screening/baseline and study period.

The MedDRA nomenclature will be used to code all adverse events. Three summary tables as shown below will be presented for TEAEs, and for a subset of TEAEs that were considered by investigator to be treatment related (ie, treatment related TEAEs).

The 3 summary tables to be generated are:

1. by preferred term in descending order of incidence rate (summarized by treatment group)
2. by preferred term within primary SOC in alphabetical order (the incidence rates of each preferred term within a primary SOC as well as overall primary SOC incidence rates will be summarized by treatment group. Primary SOC's will appear alphabetically and preferred terms within each primary SOC will be sorted by descending incidence of adverse events. If a subject has multiple reports coded to the same preferred term within a primary SOC, that subject will be counted only once for that preferred term within that primary SOC).

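### SAP 2.3.3 corrects partial severity-increase dates only when they fall too early, so a worsening recorded before an injection can be counted as treatment-emergent

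*SAP*

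**What the plan says.** SAP 2.3.3 (Time Variables) gives two parallel sets of numbered rules, one for a partial date of first increase to moderate and one for severe.

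- Rules 1 and 2 set the starting date: "if day is missing but month is not, impute the date as the 15th of the month", and "if both day and month are missing, impute the date as 15 June".
- Rule 3 looks for a date that is too early at the first injection. For moderate it applies "if imputed partial date is before the first treatment while the maximum severity during pretreatment period is mild" and moves the date to the first injection. For severe the condition is widened: "while the maximum severity during pretreatment period is mild or moderate, impute the date as the first injection date".
- Rule 4 does the same at day 180 for a date falling in period 1. For moderate it applies "while the maximum severity during study period 1 is mild, impute the date as the day 180 visit date". The severe version again allows mild or moderate.

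The same section treats a partial onset date differently. It starts from the first of the month or 01 Jan, and then moves the date later if the record shows a later onset.

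The section ends by reserving imputed adverse event dates for deciding TEAE status. Under SAP 6.2 a pre-existing event is a TEAE if it is "an adverse event with onset prior to study treatment that worsened in severity" after treatment began. A parallel definition applies to each cycle. SAP 1.1 states the use: "The primary safety analysis is the calculation of incidence of treatment emergent adverse events (TEAE) for the entire study period", and for each cycle as well.

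**The concern.** Corrections that only move a date later are complete when the starting date is the earliest one possible, as in the onset rule. The severity rules start from a mid-point, which can be wrong in either direction, yet they keep only the move-later corrections. No rule moves back a date that falls on or after an injection when the recorded maximum severity before that injection had already reached the grade.

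The imputed date can then contradict the trial's own severity record and decide TEAE status wrongly. TEAE incidence is the primary safety analysis, so the rule acts directly on the main safety tables, overall and by cycle.

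**Working it through.** The plan states no figure here, so there is nothing to reproduce. The check applies the four rules in order to worked cases and then counts when they fail.

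**Assumed dates.** First injection 10 May 2014. Day 180 visit 179 days later, 5 November 2014.

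| Case | Truth and recorded severity | Rules as written | Result |
|---|---|---|---|
| A | Moderate on 3 May, day missing; pretreatment maximum moderate | 15 May; rule 3 needs an earlier date and rule 4 a mild period 1, so neither applies | False TEAE, cycle 1 and whole study |
| B | Moderate in April, only the year known; pretreatment and period 1 maximum moderate | 15 June; no rule applies | False TEAE, cycle 1 and whole study |
| C | Mild before first injection, moderate on 2 November, day missing; period 1 maximum moderate | 15 November; no rule applies | If retreated on 5 November: false cycle 2 TEAE, lost from cycle 1 |
| D | Case A at severe grade | 15 May; no rule applies | As A |
| E | Case A, but eased to mild in period 1 | 15 May, then rule 4 moves it to 5 November because it does not look at pretreatment severity | False TEAE, in cycle 2 if retreated |
| F | Control: injection 20 May, worsened 25 May, pretreatment mild | 15 May, then rule 3 moves it to 20 May | Correct |

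In A to D the period 1 maximum is at the grade in question. Case F shows that the too-early error is handled. Cases A to E show that the too-late error is not.

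**When the failure occurs, month known.** Let the injection fall on day i and the true worsening on an earlier day of the same month. The imputed 15th is on or after the injection when i ≤ 15. Every such worsening is misdated for i from 2 to 15, and none for i above 15.

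- Share of calendar dates on days 2 to 15: 14 × 12 / 365 = 168/365 = 46.0%.
- Misdated pairs per month: the sum of (i − 1) for i = 2 to 15, which is 105.
- Pairs with worsening before injection: 378 (28-day month), 435 (30-day), 465 (31-day). Misdated share: 105/378 = 28%, 105/435 = 24%, 105/465 = 23%.
- Over a year: 12 × 105 / (7 × 465 + 4 × 435 + 378) = 1260/5373 = 23.5%, taking all such pairs as equally likely.

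**When the failure occurs, year only.** 15 June is day 166. Every worsening earlier in the injection year is misdated when the injection is on or before that date: 166/365 = 45.5% of dates.

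**These shares are conditional.** They describe worsenings already known to lie in the injection month or year. The protocol's Study Design section puts screening at day −56 to day −1. With 30-day months, a uniform injection day and worsening spread evenly over the window, the share of day-missing pretreatment worsenings that are misdated is:

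- 56-day window: 105/(30 × 56) = 6.25%
- 28-day window: 105/(30 × 28) = 12.5%
- Period 1, about 179 days, for the day 180 route: 105/(30 × 179) = 2.0%

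**Which counts move.**

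- Pretreatment route: the event becomes a TEAE that it should not be, so the whole-study count rises by one.
- Day 180 route, onset before first injection: the event was already a TEAE through its period 1 worsening. It moves from cycle 1 to cycle 2 and the whole-study count is unchanged.
- Day 180 route, onset in period 1: the event is a cycle 1 and whole-study TEAE by onset. Only a false cycle 2 TEAE is added.

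**Check of the remedy.** Start from the first of the month or 01 Jan, not before onset, then apply rule 3 and then rule 4. Cases A, D and E start at 1 May and stay pretreatment. B starts at 01 Jan, or at onset if later, and stays pretreatment. C starts at 1 November and stays in period 1. F starts at 1 May and moves to 20 May. A period 2 worsening with only the year known, mild until then, starts at 01 Jan or at onset. Rule 3 (where the date is before first treatment) and then rule 4 carry it to day 180. All are classified correctly.

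**The case against.** The other side has several fair points.

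- **The SAP has a general safeguard.** SAP 2.3.3 promises full use of partial information where sensible, and SAP 6.2 requires actual worsening. An event that never exceeded its pretreatment maximum has not worsened on the record. But the numbered rules are specific and complete in form, and the section makes the imputed date the instrument for TEAE status. A programmer who follows them gets the wrong answer in case A. The general sentence states an aim that the rules miss.
- **A mid-point is a legitimate choice.** It is, if corrections run in both directions. Here they do not.
- **The cases may be rare.** This stands. The adverse event form and its checks are not in the documents, and partial severity dates may be very few. A year-only date for a change within a screening window of at most eight weeks is the less likely scenario.
- **No safety test is affected.** This stands. SAP Amendment 1 removed p-values from the safety analysis, so the tables are descriptive.

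A reader might also infer three stronger claims that the documents do not support.

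- **That the error always adds events.** Whole-study incidence can be inflated only through the pretreatment route. The day 180 route concerns retreated subjects only, and can remove a cycle 1 TEAE as well as add a cycle 2 one.
- **That 46% or 45% of partial dates are misclassified.** Those are shares of injection dates, relevant only when the worsening lies in the injection month or year.
- **That the arms are affected unequally.** Pretreatment worsening precedes randomized treatment. A different retreated share by arm does not in itself bias a rate calculated among retreated subjects. Each dose is enrolled over about two weeks, so the misdated share could vary by cohort, but the documents give no enrolment dates from which to show it.

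**Conclusion.** Wrong as written, with a probably small effect. The severity-increase rules can date a worsening after an injection when the recorded maximum severity shows that the grade was reached before it. The result is a false TEAE for cycle 1 and the whole study, or, for a retreated subject, a false cycle 2 TEAE with a possible loss from cycle 1.

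The failure needs a partial severity-increase date and an injection on days 2 to 15 of the worsening month, or on or before 15 June of the worsening year when only the year is known. Within those conditions it is certain whenever the worsening preceded the injection. The total effect cannot be sized, because the number of partial severity dates is not given. For scale, one false event in a group of about 40 moves a preferred-term incidence by 1/40 = 2.5 percentage points.

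The percentages in the working rest on uniform injection and worsening days. The finding itself does not: it follows from the wording of the rules. No imbalance between arms is claimed.

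**What to change.** In SAP 2.3.3, for both the moderate and the severe rules, replace the 15th with the first of the month and 15 June with 01 Jan, but never earlier than the event's onset date. Keep rules 3 and 4 as they are and state that they apply in sequence. The onset floor is needed because rule 3 presupposes a pretreatment severity, which an event starting after the injection does not have. If onset is also partial, use the onset date already imputed in that section, and extend the sentence restricting its use accordingly.

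An equivalent route is to decide worsening directly from the recorded maximum severity in the pretreatment period, period 1 and period 2. Rules 3 and 4 already use the first two.

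The cost is a short SAP edit and a small programming change, with no new data. A few events would stop being TEAEs, and a few would move from cycle 2 to cycle 1.

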#### **2.3.4 Stratification**

Subject randomization is stratified by baseline MMPS (4 or 5) at baseline (day 1). In case of mis-stratification, the subjects’ actual baseline MMPS will be used for analyses.

### **2.3.5 Handling Drop-out or Missing Data**

For efficacy analyses of mITT population of the change from baseline in lower facial volume using VECTRA 3D images, MMPS, lower facial width, mandibular facial angle, CT masseter muscle volume, LFSC, and LFSQ, last observation carried forward (LOCF) will be used to impute missing values for each scheduled visit. Only missing data for visits up to day 180 of each treatment cycle will be imputed. Missing data for visits after day 180 of each cycle will not be imputed. If a subject exited the study before day 180 of a treatment cycle, visits after the study exit will not be imputed.

Missing baseline values for lower facial width, mandibular facial angle, CT masseter muscle volume, LFSC, and LFSQ will be imputed using the average of subjects with non-missing values. Missing values for change from baseline in lower facial volume using VECTRA 3D images at day 30 will be imputed using the average of subjects with non-missing values.

For angle measurements, the average degree from both sides of the face will be determined first; if the degree of angle is missing for 1 side of the face, then the angle for the subject will be based on the angle of the other side of the face. If a subject's average is a half-degree value, it will be rounded up to an integer (eg, 30.5 degree will be rounded up to 31 degrees).

For rating an individual's MMPS score, the average of the scores from both sides of the face will be determined first; if a score is missing for 1 side of the face, then the score for the subject will be based on the score of the other side of the face. If a subject's average is a half-grade value, it will be rounded up to an integer to remain consistent with the original scale (eg, 1.50 will be rounded up to 2).

When implemented, imputation of missing values will be performed only for subjects who receive a treatment in the pertinent treatment cycle. For example, only subjects receiving the second treatment will have values imputed in treatment cycle 2; subjects who discontinued from the study during the first treatment will not have any data imputed in treatment cycle 2.

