# 7.2 Collection and Derivation of Primary and Secondary Efficacy Assessments

Efficacy results for all study visits will be summarized based on time since injection. Visit windows for all timepoints will be described in the statistical analysis plan.

Pairwise comparisons will be done between each BOTOX group and the placebo group. A pairwise comparison will also be done between a BOTOX group and the next higher dose BOTOX group. For interim analyses, subjects in the placebo group(s) from previous cohort(s) will be pooled with the placebo group from the current cohort for analysis if the results for the placebo groups are combinable. For final analysis, all subjects who received placebo will be pooled together as a total placebo group if the results for the placebo groups are combinable. Details will be specified in the Analysis Plan.

The primary efficacy variable will be the lower facial volume at day 90. The change from baseline in lower facial volume will be analyzed by analysis of variance (ANOVA) with treatment and baseline (day 1) MMPS grade as factors to assess the response between groups.

For analysis of the mITT population, the last observation carried forward (LOCF) method will be used to impute missing values. For analysis of the PP population, observed data without imputation will be used.

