## 1. Introduction

This analysis plan provides an expanded and detailed description of the statistical methods presented in the Study 191622-130 protocol.

This analysis plan is based on Protocol Amendment 1, approved on 28 February 2014.

There are 4 cohorts in total to be enrolled into the study. For each cohort, there will be a database snapshot with key data through the day 90 visit, for the purpose of the Data Review Committee (DRC). There will be a final database lock with all study data after all subjects have completed the study (final cohort day 360). Subjects' treatment assignments will remain blinded for all site personnel, study subjects, and Allergan personnel directly involved with ongoing operational activities of the clinical study, until completion of the final database lock.

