## 2. Analysis Populations and Data Conventions

### 2.1 Analysis Populations

Two different analysis populations will be used in the analysis of this study.

All efficacy analyses will be performed on the modified intent-to-treat (mITT) population, consisting of all randomized subjects who received study treatment and had at least 1 follow-up visit. For the mITT population, analyses will be performed using subjects' planned treatment.

The safety analyses will be based on the safety population, which will consist of all subjects who receive at least 1 injection of study treatment. All safety analyses will be performed with subjects analyzed by their actual treatment received.

Due to missing source documents, subject [REDACTED] will be excluded from all analyses but still included in the listings.

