## **2.3 Data Conventions**

Certain data conventions and definitions are stated in this section and apply to all analyses.

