### **5.1 Collection and Derivation of Primary Efficacy Assessments**

The primary efficacy variable, change from baseline in lower facial volume (cm^3), is calculated from VECTRA M3 digital photography system 3D image models [REDACTED]

Visit windows for all time points are specified in Section 2.2. The primary time point is day 90 of the first treatment cycle.

Between group comparisons will only be performed for each BOTOX group against the placebo group, and for each BOTOX group against the next higher dose BOTOX group.

For analysis of the mITT population, the last observation carried forward (LOCF) method will be used to impute missing values.

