### **5.2 Primary Efficacy Analyses**

Descriptive statistics for change from baseline in lower facial volume for each study visit (sample size, mean, standard deviation, median, minimum, and maximum) will be provided by treatment regimen for all scheduled visits.

The primary efficacy analysis will be based on the mITT population. Day 90 is the primary timepoint.

The following set of hypotheses will be used to compare the BOTOX groups with placebo:

- Null hypothesis: BOTOX and placebo are equally effective in changing lower facial volume at day 90.
- Alternative hypothesis: BOTOX and placebo are not equally effective in changing lower facial volume at day 90.

The change from baseline in lower facial volume at each visit will be analyzed using an ANOVA model with treatment, and baseline MMPS grade as factors. In addition, 2-sided 95% confidence intervals for the treatment differences will be provided.

Analysis will also be performed based on observed data (ie, strictly data that falls within the visit windows) for the mITT population.

Among-group comparisons for the placebo groups will be analyzed using an ANOVA model with treatment as factor to test whether they are combinable. If the difference among the placebo groups are significant, sensitivity analysis will also be done for the primary variable using an ANOVA model with treatment, cohort number (as numeric variable) and baseline MMPS grade as factors.

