**11. Deviations from Protocol Section 7**

Not applicable.

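### SAP 2.3.5 fills a missing day-30 change in lower facial volume with an average whose set is not defined, and on either reading this spoils the day-30 ANOVA; the rule on visits after study exit needs only a documentation entry

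*SAP*

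**What the plan says.** **Day-30 fill.** SAP 2.3.5 has a rule for the primary variable alone. Where the change in lower facial volume is missing at day 30, it is replaced by the mean of the subjects who have that value. The text does not say whether the mean is taken within treatment arm, within MMPS grade, within cohort or over everyone. The protocol contains no such fill.

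**Use of the day-30 value.** SAP 5.2 says "The change from baseline in lower facial volume at each visit will be analyzed using an ANOVA model". The factors are arm and day-1 MMPS grade, and 95% confidence intervals are given for the differences. Day 90 of cycle 1 is the primary time point, but day 30 is tested in the same way. SAP 2.3.7 sets the level at 0.05, two-sided.

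**LOCF and study exit.** Protocol 7.2 says that for the mITT population "the last observation carried forward (LOCF) method will be used to impute missing values". SAP 5.1 has the same sentence: "For analysis of the mITT population, the last observation carried forward (LOCF) method will be used to impute missing values". SAP 2.3.5 adds limits. LOCF stops at day 180 of each cycle, and "If a subject exited the study before day 180 of a treatment cycle, visits after the study exit will not be imputed". SAP section 11, headed "Deviations from Protocol Section 7", is marked not applicable.

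**The concern.** A mean put in place of a missing value carries no new information, yet the ANOVA counts it as a measured subject. If the mean comes from the subject's own arm, the estimate is unaffected, but the within-arm spread looks too small and the sample too large. The standard error is then too low. If it comes from all subjects, the same number goes into every arm and pulls the arms together. Because the averaging set is undefined, two programmers could also produce different day-30 results from the same data.

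At stake are the day-30 differences, intervals and p-values. There is also a possible route to day 90. For a subject still in the study with no day-60 or day-90 volume, LOCF would carry the filled value forward to the primary time point.

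The exit rule raises a separate question of clarity. The mITT population is defined as "consisting of all randomized subjects who received study treatment and had at least 1 follow-up visit". A subject who leaves before day 90 with no value in the day-90 window is therefore in mITT but not in the day-90 ANOVA. A reader of Protocol 7.2 or SAP 5.1 alone would not expect that.

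**Working it through.** **Inputs.** Each BOTOX arm has 40 subjects (Protocol 7.5). Placebo has 4 × 10 = 40 once pooled (SAP section 5). The test is two-sided at 0.05. The number filled per arm, k, is an assumption: 1, 2, 4 or 6 of 40, equal in both arms, with values missing at random. Let m = 40 − k. The plan gives no figure for this point. Its stated power of 93% (40 against 10, effect size 1, one-sided 0.10) reproduces as 93.6% by the noncentral t, but nothing below depends on it.

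**1. Day 30, arm mean.** The arm mean still rests on m values, so its true variance is σ²/m. The ANOVA divides the same sum of squares, (m − 1)s², by 39 and then by 40. The ratio of estimated to true standard error is √[(m − 1)m/(39 × 40)]. The critical value for 78 df is 1.991. The type I error is the two-sided tail of a t with 2(m − 1) df beyond 1.991 times that ratio.

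| k | SE ratio | effective cut-off | df | type I error |
|---|---|---|---|---|
| 1 | 0.975 | 1.940 | 76 | 5.6% |
| 2 | 0.949 | 1.890 | 74 | 6.3% |
| 4 | 0.899 | 1.789 | 70 | 7.8% |
| 6 | 0.848 | 1.688 | 66 | 9.6% |

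**2. Day 30, overall mean.** The same number A is put into both arms. The estimated difference is (m/40)·(observed difference) + (k/40)·(A − A), so it shrinks by k/40: 2.5, 5, 10 or 15%. This does not depend on the dose mix or on A, provided the filled share is equal in the two arms. When there is no treatment effect, the ratio of estimated to true variance is 40(m − 1)/(39m), which is 0.999, 0.999, 0.997 and 0.996. Type I error therefore stays near 5%. The harm is to the estimate and its interval.

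**3. Carry-forward to day 90.** The fill reaches day 90 only for a subject who lacks days 30, 60 and 90. If visits are missed independently at an assumed 10% or 20%, the share is 0.1³ = 0.1% or 0.2³ = 0.8%. Simulation (effects of 60, 90 and 100% of full size at days 30, 60 and 90; visit correlation 0.7) gives day-90 type I error of 5.0% or 5.1% with an arm mean. The estimate moves by less than 0.01 SD against LOCF without the fill. If 1 of 40 per arm were nevertheless filled and carried, type I error would be about 5.4% with an arm mean, and the difference would shrink by about 1% (arm mean) or 2.5% (overall mean).

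**4. Exit rule.** Assume a true day-90 difference of −1.0 SD, visit correlation 0.7 and exit between days 60 and 90. A range covers two assumed strengths of dependence of exit on response.

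| Assumed exit pattern (BOTOX / placebo) | Exits left out | LOCF |
|---|---|---|
| unrelated to response, 10% / 10% | −1.00 | −0.99 |
| low responders, 5% / 15% | −0.94 to −0.92 | −1.01 to −1.02 |
| low responders leave BOTOX only, 15% / 5% | −1.09 to −1.12 | −0.95 to −0.94 |
| strong responders leave BOTOX only, 15% / 5% | −0.91 to −0.88 | −1.02 to −1.03 |

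For exit between days 30 and 60, LOCF ranges from −0.89 to about −1.01. Over all scenarios the largest error is about 0.12 SD with exits left out and about 0.11 SD with LOCF.

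**The case against.** **On the fill.** It has a plausible purpose. Protocol 12.1.2 measures volume only as the difference between a baseline and a post-treatment surface, and day 30 is the first scheduled clinic visit after treatment. LOCF therefore has no earlier value to carry. Day 30 is not the primary visit, and with one missing value per arm the type I error is only 5.6%. These points stand and limit the importance of the matter. They do not make the fill sound, because a subject with no measurement can simply be left out of that visit's ANOVA.

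**On the exit rule.** A reader might infer that the SAP breaches the protocol and that leaving early exits out biases the primary result. The documents do not support this. Protocol 7.2 and SAP 5.1 share one general sentence. If SAP 2.3.5 may refine it in SAP 5.1, it may refine it in the protocol too. The SAP says "This analysis plan provides an expanded and detailed description of the statistical methods presented in the Study 191622-130 protocol" and, of its data conventions, "Certain data conventions and definitions are stated in this section and apply to all analyses". The rule is stated openly under a heading on drop-out. Protocol 8.8 calls for exit procedures, which may give some early leavers a value in the day-90 window; the windows are not in the supplied text. Nor is LOCF shown to be better. What stands is that the limit is missing from SAP 5.1 and from section 11.

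**Conclusion.** The point holds for the day-30 ANOVA. The fill is undefined, and each reading damages a planned analysis: type I error of about 5.6 to 9.6% with an arm mean, or a difference shrunk by about 2.5 to 15% with an overall mean, for 1 to 6 of 40 filled per arm. The sizes rest on assumed counts and on equal missingness in the two arms.

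A reader might infer that the primary day-90 test is compromised. That does not follow. Under independent misses the effect there is negligible. Misses that cluster in the same subjects would raise it, but the documents give no sign of how often that would happen.

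The exit rule is a documentation gap only. Any bias from leaving early exits out depends on why subjects leave. It is zero if exit is unrelated to outcome, and LOCF can err by a similar amount.

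**What to change.** 1. In SAP 2.3.5, delete the day-30 average fill for change in lower facial volume. A subject with no post-treatment volume then has no day-30 value, and nothing artificial is carried forward. Defining the averaging set would remove the ambiguity but not the error.
2. In SAP 5.1, cross-refer to the exit rule in SAP 2.3.5, so that a reader can see who may be absent from the day-90 ANOVA. List that rule in SAP section 11.

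A repeated-measures model (MMRM) on the observed day-30, 60 and 90 changes could be added as a sensitivity analysis, but it is optional.

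The cost is a few lines of SAP text; no new data are needed and the primary ANOVA is unchanged. The downside is that subjects without a day-30 volume drop out of the day-30 ANOVA, so its intervals are slightly wider. The standard error grows by √(40/m) relative to complete data, or about 1.3, 2.6, 5.4 and 8.5% for k = 1, 2, 4 and 6. That width reflects the information actually collected.
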